13.4. Reporting Adverse Events

The Investigator will notify the Sponsor of an adverse event by e-mail, facsimile, or telephone as soon as possible and no later than 24 hours from discovery for any serious /significant adverse events, and 2 days from discovery for any non-significant adverse event. In addition, a written report will be submitted by the Principal Investigator to the IEC/IRB according to their requirements (section 13.4.2). The report will comment whether the adverse event was considered to be related to the test article, study treatment or study procedures.

13.4.1. Reporting Adverse Events to Sponsor

Serious/Significant Adverse Events

The Investigator will inform the sponsor of all serious/significant adverse events occurring during the study period as soon as possible by e-mail or telephone, but no later than 24 hours following discovery of the event. The Investigator is obligated to pursue and obtain information requested by the Sponsor in addition to that information reported on the eCRF. All subjects experiencing a serious/significant adverse event must be followed up and all outcomes must be reported.

When medically necessary, the Investigator may break the randomization code to determine the identity of the treatment that the subject received. The Sponsor and study monitor should be notified prior to unmasking the test articles.

In the event of a serious/significant adverse event, the Investigator must:

- Notify the Sponsor immediately.
- Obtain and maintain in the subject's records all pertinent medical information and medical judgment for colleagues who assisted in the treatment and follow-up of the subject.
- Provide the Sponsor with a complete case history which includes a statement as to whether the event was or was not related to the use of the test article.
- Notify the IEC/IRB as required by the IEC/IRB reporting procedure according to national regulations.

Unanticipated (Serious) Adverse Device Effect (UADE)

In the event of an Unanticipated (Serious) Adverse Device Effect (UADE), the Investigator will submit a report of the UADE to the Sponsor and IEC/IRB as soon as possible, but no later than 24 hours after the Investigator first learns of the effect. This report is in addition to the immediate notification mentioned above.

The Sponsor must conduct an evaluation of the UADE and must report the results of the evaluation to FDA, the IEC/IRB and participating Investigators within 10 working days after the Sponsor first receives notification of the effect.

Non-Serious Adverse Events

All non-serious adverse events, including non-serious adverse device effects, will be reported to the sponsor by the Investigator no later than 2 days from discovery.

13.4.2. Reporting Adverse Events to the Responsible IEC/IRB and Health Authorities

Adverse events that meet the IEC/IRB requirements for reporting must be reported within the IEC/IRB's written guidelines. Each clinical site will refer to and follow any guidelines set forth by their Approving IEC/IRB. Each clinical site will refer to and follow any guidelines set forth by their local governing Health Authorities.

The Sponsor will report applicable Adverse Events to the local health authorities according to the written guidelines, including reporting timelines.

13.5. Event of Special Interest

None.

13.6. Reporting of Pregnancy

Subjects reporting pregnancy (by self-report) during the study will be discontinued after the event is recorded as an Adverse Event. Once discontinued, pregnant participants and their fetuses will not be monitored for study related purposes. Pregnant participants are not discontinued from contact lens or solution related studies for safety concerns, but due to general concerns relating to pregnancy and contact lens use. Specifically, pregnant women are discontinued due to fluctuations in refractive error and/or visual acuity that occur secondary to systemic hormonal changes, and not due to unforeseen health risks to the mother or fetus.

14. STATISTICAL METHODS

14.1. General Considerations

Statistical Analysis will be undertaken by the sponsor or under the authority of the sponsor. A general description of the statistical methods to be implemented in this clinical trial is outlined below.

Descriptive statistics will be reported for all key variables as appropriate. Continuous data will be summarized descriptively by sample size (n), mean, standard deviation (SD), median, minimum (Min) and maximum (Max). Categorical data will be summarized descriptively by frequency count (n) and percentage (%) of subjects or eyes within each category level. Summary tables will be presented by event (Baseline, Fitting, 1-week follow-up, 2-week follow-up, Unscheduled and Final Evaluations) and study lens type (Test and Control) as applicable, for the analysis set of interest. The denominator for all percentages will be the number of subjects (or eyes as applicable) with available data in the lens group under consideration. Unscheduled visits and tele-visits will be summarized separately and will be excluded from the primary and secondary analysis.

All available data collected at scheduled visits will be used in the statistical summaries and analyses, with no imputation of missing data. Unscheduled visits will be summarized separately and will be excluded from the statistical analysis. All data summaries and statistical analyses will be performed using the SAS software Version 9.4 or higher (SAS Institute, Cary, NC).

14.2. Sample Size Justification

This study was not designed or powered to test any statistical hypotheses with respect to incidence (percentage) of study lens-related grade 3 or higher SLFs after approximately 2-weeks of lens wear. Instead, the sample size and study design were based on clinical considerations and operational feasibility. A sample size of 60 subjects (120 eyes) to complete (through Visit 6), will provide adequate precision around the estimate of the percentage of eyes with study lens related grade 3 or higher SLFs as measured by the half-width of a 95% CI. Percision estimates were provided using difference scenarios for the percentage of events and are displayed in Table 7 below.

Table 7: Half-Width of the 95% Confidence Intervals for Proportion of Eyes with Grade 3+ SLFs

Sample Size (number of subject to complete)	Proportion of Grade 3 + SLFs	Confidence Interval Half-Width	Estimated Upper Limit
60 (120 eyes)	0 (no events)	0.02466	0.02466
	0.0083 (1 event)	0.03057	0.03887
	0.0167 (2 events)	0.03488	0.05158

A total of 60 subjects are targeted to complete the study. To account for subject drop-out approximately 66 (based on a drop-out rate of 10%) subjects will be enrolled in this study to ensure that at least 60 subject complete the study.

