14.5. Primary Analysis

The summary of the primary endpoint will be conducted on the safety population.

The distribution of eyes (n, %) with SLF grade level will be summarized by study lens type. The grading SLFs scale is from 0 to 4, where Grade 0 represents the absence of findings and 1 to 4 representing successively worse findings (i.e., Grade 1 = trace, Grade 2 = Mild, Grade 3 = moderate and Grade 4 = severe).

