14.7. Exploratory Analyses

Summary for exploratory endpoints will be provided for both the ITT and the Per-Protocol populations. However, all analyses for exploratory endpoints will be conducted on the ITT population.

Distance Monocular HLHC logMAR visual acuity

Distance monocular HLHC logMAR visual acuity at the 1-week follow-up will be summaried and presented only descriptively by lens type accompanied with the 2-sided 95% CIs. Summary statistics are described in section 14.1.

CLUE Comfort, Vision, and Handling Scores

The analysis of exploratory endpoints of CLUE comfort, vision and handling at the fitting, 1-, and 2-week follow-up visits will be conducted separately for each CLUE domain. The exploratory analysis of each CLUE score endpoints will include the estimation of mean CLUE scores and associated 95% CIs for each study lens (Test lens and Control lens). Additionally, the mean difference between the Test and Control lens paired with the 95% CI will be calculated.

CLUE scores will be analyzed using a linear mixed model, adjusting for baseline scores as a covariate. Sequence of lens wear, study period, lens type (Test and Control), timepoint (fitting, 1-week, and 2-week follow-up visit), and the ineraction lens type by timepoint will be included as fixed effects. Other baseline characteristics such age, gender, and/or race will be included as fixed covariates when appropriate. Site and subject nested within site will be included as random effects (G-side). Residual errors from measurements within the same subject and timepoint across study period will be modeled using an unstructured covariance structure (UN). If the model does not converge, other covariance structures will be considered. The Kenward and Roger method will be used for the denominator degree of freedom. Estimates for each study lens and between study lenses (Test lens and Control lens) will be carried out using two-sided 95% CIs for the least-square mean and/or mean difference.

Toric Lens Orientation

The distribution (counts, percentages) of eyes for the toric Orientation (in degrees) at 1- and 3-minutes after lens insertion will be summarized by timepoint (fitting, 1-, and 2-week follow-up) and lens type.

Mean Settled Lens Orientation

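### Table 7 is labelled as 95% CI half-widths but holds one-sided 95% exact upper limits and their distance from the estimate, with method, sidedness and eye independence unstated

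*Combined protocol and SAP*

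**What the plan says.** Section 14.2 explains that no hypothesis is tested and that "the sample size and study design were based on clinical considerations and operational feasibility". It then makes a precision statement: "A sample size of 60 subjects (120 eyes) to complete (through Visit 6), will provide adequate precision around the estimate" of the primary percentage, "as measured by the half-width of a 95% CI". The supporting table is headed "Table 7: Half-Width of the 95% Confidence Intervals for Proportion of Eyes with Grade 3+ SLFs". It has one row each for 0, 1 and 2 events in 120 eyes:

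| Events (proportion) | Half-width column | Upper-limit column |
|---|---|---|
| 0 (0) | 0.02466 | 0.02466 |
| 1 (0.0083) | 0.03057 | 0.03887 |
| 2 (0.0167) | 0.03488 | 0.05158 |

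The section names no interval method, does not say whether the interval is one- or two-sided, and makes no statement about correlation between the eyes of one subject. Section 14.5 plans no interval for the primary endpoint: "The distribution of eyes (n, %) with SLF grade level will be summarized by study lens type". Sidedness appears only for exploratory endpoints in section 14.7. For the CLUE scores, for example, estimates "will be carried out using two-sided 95% CIs for the least-square mean and/or mean difference".

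**The concern.** A half-width is half the distance between the lower and upper limits, so the term implies a two-sided interval. The zero-event row cannot fit that meaning. The lower limit there is 0, so the half-width must be half the upper limit, yet both columns show 0.02466.

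The study exists to estimate the primary percentage (section 2.1), and Table 7 is the only numerical support for the claim that 60 completers give enough precision. A reader who takes the limits as two-sided 95% limits sees values that are too favourable for a safety endpoint. A reader who takes the half-widths literally sees values that are too large. Because section 14.5 plans no interval, nothing later in the plan shows which one was meant, and the reported interval could differ from the one used to justify precision.

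**Working it through.** **Inputs.** From section 14.2: n = 120 eyes (60 subjects), printed proportions p = 0, 0.0083 and 0.0167, confidence level 95%. From section 5.1: lenses are worn bilaterally, so each subject contributes two eyes. The documents give no between-eye correlation.

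**1. Reproduce the table.** The one-sided 95% Clopper-Pearson upper limit is U = Beta⁻¹(0.95; x+1, n−x). Put in n = 120 and x = 120 × p, which gives x = 0, 0.996 and 2.004:

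| p | U | U − p | Table 7 (limit; half-width) |
|---|---|---|---|
| 0 | 0.02466 | 0.02466 | 0.02466; 0.02466 |
| 0.0083 | 0.03887 | 0.03057 | 0.03887; 0.03057 |
| 0.0167 | 0.05158 | 0.03488 | 0.05158; 0.03488 |

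All six figures agree to five decimals. Whole counts of 1 and 2 give 0.03892 and 0.05153, so the table was computed from the rounded proportions. That difference is about 0.00005 and immaterial.

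**2. Check the tail.** The binomial probability of x or fewer events, with n = 120 and the true proportion equal to the printed limit, is 0.0500, 0.0503 and 0.0498 for x = 0, 1 and 2. A two-sided 95% exact limit needs 0.025.

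**3. Two-sided exact intervals for whole counts, n = 120.** The upper limit is Beta⁻¹(0.975; x+1, 120−x). The lower limit is Beta⁻¹(0.025; x, 121−x), or 0 when x = 0. The half-width is (upper − lower)/2.

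| Events | 95% interval | Half-width | Upper limit − estimate | Upper limit − Table 7 limit |
|---|---|---|---|---|
| 0 | 0 to 0.03027 | 0.01514 | 0.03027 | 0.0056 |
| 1 | 0.00021 to 0.04556 | 0.02267 | 0.03722 | 0.0067 |
| 2 | 0.00202 to 0.05891 | 0.02844 | 0.04224 | 0.0073 |

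The two-sided 90% exact interval shares its upper limit with the one-sided 95% bound, but its half-widths are 0.01233, 0.01925 and 0.02428. The printed half-widths match neither set. Wald, Wilson, Agresti-Coull and Jeffreys half-widths, at 95% and 90% and with n = 120 or n = 60, do not reproduce the column either.

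**4. Between-eye correlation (assumed values).** Table 7 is reproduced with n = 120 and not with n = 60, so it treats the eyes as independent. With two eyes per subject, take an effective n of 120/(1+ρ). The zero-event limits are then 1 − 0.05^(1/n) one-sided and 1 − 0.025^(1/n) two-sided:

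| Assumed ρ | Effective n | One-sided 95% | Two-sided 95% |
|---|---|---|---|
| 0 | 120 | 0.0247 | 0.0303 |
| 0.5 | 80 | 0.0368 | 0.0451 |
| 1 | 60 | 0.0487 | 0.0596 |

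**The case against.** The strongest reply is that the calculation is sound: these are correct values of a recognised one-sided bound, so the fault lies in the labels. That stands. If a one-sided bound was intended, no limit needs to change. Two-sidedness for the primary percentage is an inference from the word half-width and from the exploratory endpoints, which are continuous; the plan does not state it.

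On the plan's own measure, the true two-sided half-widths (0.0151, 0.0227, 0.0284) are also smaller than those printed, so with independent eyes the label does not exaggerate precision. Only the upper-limit column looks favourable, and only when read as two-sided. A careful reader can see that each limit equals the proportion plus the half-width column, although not which method or sidedness lies behind it.

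Little depends on the table. The size was set on other grounds, no hypothesis is tested, and no threshold defines adequate precision. This limits the consequence, but it does not make the label right where the table is the only numerical support for an estimation endpoint.

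The row heading does show 120 eyes, so the unit is disclosed, though independence is not. The correlation figures rest on assumed values, and the effective-n substitution is an approximation at ρ = 0.5.

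**Conclusion.** The point holds. Table 7 does not contain what its title and the text of section 14.2 say it contains. The mismatch is certain because all six figures are reproduced exactly as one-sided 95% exact limits and their distances from the estimate.

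Its size depends on what was meant. If a two-sided 95% exact interval was meant, the printed upper limits are too low by 0.0056, 0.0067 and 0.0073, assuming 120 independent eyes. If a one-sided bound was meant, the error is confined to the labels. In both cases the half-width column is misnamed, and the method, sidedness and independence assumption are missing.

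At the extreme of perfect correlation between eyes, the zero-event limit is about double its independent-eye value (0.0487/0.0247 = 1.97 one-sided; 0.0596/0.0303 = 1.97 two-sided). The true correlation is unknown, so this marks a range and is not an estimate. The sample size and the conduct of the trial are unaffected.

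**What to change.** Choose one interval and use it in both section 14.2 and section 14.5.

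- **Option A, two-sided 95% exact:** restate the upper limits as 0.0303, 0.0456 and 0.0589. Rename the half-width column as the distance from the estimate to the upper limit, with values 0.0303, 0.0372 and 0.0422.
- **Option B, one-sided 95% exact:** keep the approach and relabel the columns as the one-sided 95% exact upper bound and the distance from the estimate to that bound. Compute from whole counts, which gives bounds of 0.0247, 0.0389 and 0.0515.

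Under either option:

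- name the method and sidedness in section 14.2, and align the table title and the sentence that introduces it;
- add the matching interval for the primary percentage, per lens, to section 14.5;
- state that the table assumes the two eyes of a subject are independent, and show the perfect-correlation extreme beside it (zero events, n = 60: 0.0596 two-sided or 0.0487 one-sided).

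The cost is a corrected table, its labels and a few sentences. Option A makes the stated limits slightly less favourable. Enrolment does not change under either option.

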14.3. Analysis Populations

Safety Population:

All subjects who are administered at least one treatment (study lens). Subject will be analyzed per actual treatment received.

Per-Protocol Population:

All subjects who successfully complete all visits and do not substantially deviate from the protocol as determined by the trial cohort review committee prior to database hard lock. Justification for the exclusion of subjects with protocol deviations from the per-protocol population set will be documented in a memo to file.

Intention-to-Treat (ITT) Population:

All randomized subjects. Subject will be analyzed per planned randomized treatment.

14.4. Level of Statistical Significance

Not applicable, there is no planned hypothesis testing for any endpoints in this study.

14.5. Primary Analysis

The summary of the primary endpoint will be conducted on the safety population.

The distribution of eyes (n, %) with SLF grade level will be summarized by study lens type. The grading SLFs scale is from 0 to 4, where Grade 0 represents the absence of findings and 1 to 4 representing successively worse findings (i.e., Grade 1 = trace, Grade 2 = Mild, Grade 3 = moderate and Grade 4 = severe).

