1. INTRODUCTION AND BACKGROUND

DAILIES TOTAL1® for Astigmatism Contact Lenses (DT1fA) are single-use, daily disposable lenses indicated for the correction of astigmatism and associated ametropia in persons with non-diseased eyes. The purpose of this study is to evaluate the ocular physiological response following wear of a daily disposable, toric lens design in senofilcon A incorporating a HEVL-filtering chromophore (RTY-1) relative to DT1fA as Control.

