2. STUDY OBJECTIVES, ENDPOINTS AND HYPOTHESES

2.1. Objectives

Primary Objective:

The primary objective of this study is to estimate the incidence rate (percentage) of eyes with clinically significant slit-lamp findings (Grade 3 or 4) related to each study lens (Test lens and Control lens) after approximately 2-weeks of lens wear.

Exploratory Objectives:

The exploratory objectives of this study include the estimation of the mean difference between study lenses (Test lens and Control lens) with respect to distance monocular high luminance, high contrast (HLHC), logMAR visual acuity (at the 1-week follow-up visit), and CLUE comfort, vision, and handling scores (at the fitting, 1- and 2-week follow-up visits). Additional exploratory objectives of the study are to estimate the mean and standard deviation of the settled toric roation of each study lens (Test lens and Control lens) following lens settling and after 1- and 2-weeks of lens wear, and to assess the toric lens orientation of each study lens, 1- and 3-minutes after lens insertion. Adverse events will also be monitored and collected.

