2.3. Hypotheses

Not applicable, there is no planned hypothesis testing for any endpoints in this study.

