4.2. Study Design Rationale

A 6-visit, double-masked, 2×2 crossover study design was chosen to demonstrate the study objectives. In this design, each subject will act as their own control to reduce the influence of potential confounding factors such as age, gender, race, and vision correction. To help further reduce the potential for carryover effects, a washout period of approximately 1-week (7 ± 2 days) between study will be used.

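### Section 1 states a purpose relative to Control, but the primary objective and analysis are per-lens, so the primary safety endpoint gets no Test-Control estimate or interval

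*Combined protocol and SAP*

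**What the plan says.** - **Purpose (Section 1).** "The purpose of this study is to evaluate the ocular physiological response following wear of a daily disposable, toric lens design in senofilcon A", and the sentence ends "incorporating a HEVL-filtering chromophore (RTY-1) relative to DT1fA as Control".
- **Design rationale (4.2).** In the crossover, "each subject will act as their own control to reduce the influence of potential confounding factors such as age, gender, race, and vision correction".
- **Primary objective (2.1).** The aim is "to estimate the incidence rate (percentage) of eyes with clinically significant slit-lamp findings (Grade 3 or 4) related to each study lens". No difference is named. The exploratory objectives in the same section do name a mean difference between lenses.
- **Hypotheses (2.3, repeated in 14.4).** "Not applicable, there is no planned hypothesis testing for any endpoints in this study".
- **Primary analysis (14.5).** "The summary of the primary endpoint will be conducted on the safety population", and "The distribution of eyes (n, %) with SLF grade level will be summarized by study lens type". The rest of the section describes the grading scale.
- **Other analyses.** Section 14.6 is marked not applicable. Section 14.7 plans Test-Control differences with 95% confidence intervals for CLUE scores and mean settled orientation, and none for slit-lamp findings.
- **Precision (14.2, Table 7).** Limits are given for one proportion at a time.

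**The concern.** Readers who take Section 1 at its word will set the two percentages side by side. The plan gives them no estimate of the difference and no statement of how large an excess on Test the data still allow. Equal percentages of zero could be taken as showing no difference, when with about 60 subjects they leave several points open in either direction. The absence of hypothesis tests does not explain the omission. It covers every endpoint, and two exploratory endpoints still get an estimated difference with an interval.

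**Working it through.** **1. The plan's own figure.** Table 7 gives upper limits of 0.02466, 0.03887 and 0.05158 for 0, 1 and 2 events in 120 eyes. The exact one-sided 95% upper limit with eyes taken as independent reproduces them closely. For 0 events it is 1 - 0.05^(1/120) = 0.02466; for 1 and 2 events it is 0.03892 and 0.05153. These limits concern a single proportion. No figure in the plan concerns a difference.

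**2. Which subjects a difference can use.** In Section 7.2, steps 2.9 (also used for Visit 5), 4.5 and 6.11 say that a finding of Grade 3 or worse means discontinuation; the readable part of Visit 3 agrees. A subject with such a finding on the first lens therefore never wears the second. Two consequences follow:
- An interval limited to subjects who wore both lenses would lose first-period events by design.
- A subject stopped at the 1-week visit has no 2-week record, so the definition must say that the finding counts. Section 14.1 also keeps unscheduled visits out of the analysis, so findings first seen there need the same statement.

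**3. Illustrative precision.** The documents give no expected counts, so these are assumed. The unit is the subject (either eye affected). The lenses are treated as independent samples of equal size n, between the 60 completers and the 66 enrolled in 14.2. The method is the Newcombe score interval built from Wilson limits, with z² = 3.8415.

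*No events on either lens.* The limits are ±z²/(n + z²).
- n = 60: 3.8415/63.8415 = ±6.0 points.
- n = 66: 3.8415/69.8415 = ±5.5 points.

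*One event on Test, none on Control, n = 60.* The Wilson limits are 0.00295 to 0.08855 for Test (1/60 = 0.01667) and 0 to 0.06017 for Control.
- Lower: 0.01667 - √[(0.01667 - 0.00295)² + 0.06017²] = -0.0450.
- Upper: 0.01667 + (0.08855 - 0.01667) = 0.0886.
- Result: +1.7 points (-4.5 to +8.9). The same steps at n = 66 give +1.5 points (-4.1 to +8.1).

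*First period only, no events, 33 per sequence (66/2, equal allocation assumed).* 3.8415/36.8415 = ±10.4 points.

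**4. Allowing for pairing or counting eyes.** With 60 subject pairs, the Newcombe paired interval gives ±6.0 points at no events and +1.7 (-4.5 to +8.9) at one event on Test, so the independence simplification costs nothing visible at these counts. Treating 120 eye pairs as independent would give ±3.1 points at no events, but this ignores that two eyes belong to one subject.

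**The case against.** The strongest reply is that the protocol names a difference where it wants one and does not name one here. The primary objective is per-lens, the sizing is for one proportion, and 14.5 delivers what 2.1 asks for. The comparative wording is one phrase in the background section. This stands, and it limits the point to a mismatch of purpose and objective.

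Three stronger readings are tempting, and the documents do not support them.
- *That 14.5 fails its objective.* It matches 2.1.
- *That the crossover or the control lens is wasted.* The exploratory models use the within-subject structure and give Test-Control differences. Having largely the same people under both lenses also serves the reduction of confounding claimed in 4.2.
- *That readers would see nothing but two percentages.* Section 14.5 tabulates the full grade distribution. Section 7.2 requires a Grade 3 or worse finding after dispensing to be recorded as an adverse event, and 14.7 lists every adverse event with treatment, causality and severity. With a handful of cases, each can be inspected.

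It can also be said that the interval has little decision value: there is no margin or test, and at no events it depends only on the denominators. That is fair as to its use for decisions. It does not remove the benefit of stating the uncertainty beside a comparison that Section 1 invites; neither the grade table nor the listing does so.

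**Conclusion.** The point holds as a mismatch: the purpose is relative, the primary objective and analysis are per-lens, and nothing elsewhere supplies a Test-Control estimate for slit-lamp findings. It should be corrected, but it is not an error in carrying out the stated objective. In size, about 5.5 to 6 points in either direction would remain open with no events on either lens, and an excess on Test of up to about 8 to 9 points with one event on Test alone. These figures rest on assumed counts, 60 to 66 subjects per lens, the subject as unit, and the lenses treated as independent samples. The first-period figure of ±10.4 points also assumes equal allocation. Any such estimate is descriptive only.

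**What to change.** Add to 14.5, labelled as estimation with no test:
- The Test-minus-Control difference in the percentage of subjects with a lens-related Grade 3 or higher finding in either eye, with a two-sided 95% score-type confidence interval.
- The denominator for each lens: all safety-population subjects exposed to that lens.
- A sentence that findings leading to discontinuation before the 2-week visit count as events.
- As support only, the randomised first-period difference with its interval.

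Do not restrict the main estimate to subjects who wore both lenses.

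The cost is a few table rows and sentences, with no added subjects, visits or data. The downside is a visibly wide interval.

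If the sponsor wants no relative statement on this endpoint, the alternative is to reword the purpose in Section 1 as per-lens estimation.
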